## 11.2 Secondary outcome

The secondary outcome variable is the percentage of subjects able to self-administer safe and effective injections using the given device at DV0002 Baseline (first self-injection visit). Safe and effective self-injection will be evaluated by the study personnel. The secondary outcome variables will be analyzed in the same manner as the primary outcome variable.

All data to assess the secondary outcome is collected on Subject self-injection of Bimekizumab CRF page for DV0002 Baseline.

## 11.3 Other outcomes

The other outcome variables will be summarized using descriptive statistics and they will be tabulated separately for each device overall based and within each device by P5014 treatment.

Assessments where the self-injection was not performed by the subject will be not included in any summary statistics.

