4.1.3 Other variables

4.1.3.1 Outcome variables

The other outcome variables are:

- Responses to pre-injection SIAQ (versions 2.0 and 2.1) at DV0002 Baseline.
Whenever SIAQ is assessed, version 2.0 of the SIAQ will be used to assess bimekizumab-SS-1mL and bimekizumab-SS-2mL and version 2.1 of the SIAQ will be used to assess bimekizumab-AI-1mL and bimekizumab-AI-2mL (see Section 9.1).
- Responses to post-injection SIAQ (versions 2.0 and 2.1) by visit following self-injection using the assigned device at DV0002 Baseline and Week 8.
- Injection site pain (using a VAS; 100mm) by visit after self-injection using the assigned device at DV0002 Baseline and Week 8.
- Percentage of used devices identified as having structural or mechanical integrity issues after completion of self-injection. This is based on a visual examination of the device that shows clear evidence of damage and/or compromised structural or mechanical integrity.

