13.4 Termination of the study

UCB reserves the right to temporarily suspend or prematurely discontinue this study either at a single site, multiple sites, or at all sites at any time for reasons including, but not limited to, safety or ethical issues, inaccurate or incomplete data recording, noncompliance, or unsatisfactory enrollment with respect to quality or quantity.

The study may also be temporarily suspended or prematurely terminated in either of the following situations:

- Severe or serious injection site reaction (eg, bleeding, bruising, pain) that, in the opinion of the Investigator, the overseeing IRB, or the Sponsor, is likely to be seen in other enrolled subjects who have not yet been injected with bimekizumab.
- Unexpected device malfunction leading to a failed or incomplete injection, or resulting in an SAE that, in the opinion of the Investigator, the overseeing IRB, or the Sponsor, is likely to be seen in other enrolled subjects who have not yet been injected with bimekizumab.

If the study is prematurely terminated or suspended, UCB (or designee) will inform the Investigator/institutions and the regulatory authority(ies) of the termination or suspension and the reason(s) for the termination or suspension, in accordance with applicable regulatory requirement(s). The IRB should also be informed and provided with reason(s) for the termination or suspension by the Sponsor or by the Investigator/institution, as specified by the applicable regulatory requirement(s). In addition, arrangements will be made for the return of all unused IMP and other material in accordance with UCB procedures for the study.

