### **2.2.3 Other variables**

#### **2.2.3.1 Outcome variables**

The other outcome variables are:

- Responses to pre-injection SIAQ (versions 2.0 and 2.1) at DV0002 Baseline.  
Whenever SIAQ is assessed, version 2.0 of the SIAQ will be used to assess bimekizumab-SS-1mL and bimekizumab-SS-2mL and version 2.1 of the SIAQ will be used to assess bimekizumab-AI-1mL and bimekizumab AI 2mL.
- Responses to post-injection SIAQ (versions 2.0 for bimekizumab-SS-1ml and 2.1 for bimekizumab-1ml-AI) by visit following self-injection using the assigned device at DV0002 Baseline and Week 8.
- Injection site pain (using a VAS; 100mm) by visit after self-injection using the assigned device at DV0002 Baseline and Week 8.

- Percentage of used devices identified as having structural or mechanical integrity issues after completion of self-injection. This is based on a visual examination of the device that shows clear evidence of damage and/or compromised structural or mechanical integrity.

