### **11.3.4 Structural and mechanical integrity of the devices**

The structural and mechanical integrity of the device after completion of self-injection will be assessed by the investigate after each injection in the "subject self-injection of bimekizumab" CRF page. The assessment will be done using the questions for structural integrity and function compromise. The structural integrity is based on a visual examination of the device that shows clear evidence of damage, compromised structural integrity not superficial and/or cosmetic imperfections. The functional compromise will be based on a visual examination of the device that shows clear evidence of damage and/or device dose not function normally. Both questions will be separately summarized.

Two injections will be performed at each self-injection visit. At each injection the device could be replaced. Percentages will be based on the total number of devices used.

Frequency tables will be produced to show the number and percentage of devices with:

- used bimekizumab-SS-1mL, bimekizumab-AI-1mL, bimekizumab-SS-2mL and bimekizumab-AI-2mL syringes identified as having structural integrity issues after completion of self-injection.
- used bimekizumab-SS-1mL, bimekizumab-AI-1mL, bimekizumab-SS-2mL and bimekizumab-AI-2mL syringes identified as functionally compromised.

The 90% CIs based on the Exact Binomial method will be reported as well.

---

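### The SAP does not say whether its exclusion of injections not performed by the subject (11.3) or its all-devices-used denominator (11.3.4) governs the device-integrity percentage, and the first can bias it downward

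*SAP*

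**What the plan says.** SAP 11.3 is the parent section for the other outcomes: pre-injection SIAQ, post-injection SIAQ, injection-site pain, and structural and mechanical integrity. It carries one general rule: "Assessments where the self-injection was not performed by the subject will be not included in any summary statistics". No subsection is exempted.

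Device integrity belongs to this group. SAP 2.2.3.1 defines the variable as "Percentage of used devices identified as having structural or mechanical integrity issues after completion of self-injection", and Protocol 4.1.3.1 uses the same wording.

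SAP 11.3.4 then gives its own counting rule. Integrity is recorded after each injection on the self-injection CRF page. Replacement is foreseen: "At each injection the device could be replaced". The denominator is stated directly: "Percentages will be based on the total number of devices used". Two tables are planned with 90% exact binomial intervals. The structural table counts "syringes identified as having structural integrity issues after completion of self-injection". The entry for functionally compromised devices has no such completion condition.

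Protocol 9.3 has site staff inspect used devices and sets no condition on who gave the injection.

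**The concern.** For a measure of the subject's experience or ability, it makes sense to leave out injections given by someone else. Damage to a device does not depend on who held it. A damaged or malfunctioning device is also a reason for someone else to take over, so the exclusion can select against the failures that the outcome is meant to count.

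The plan foresees the ingredients of this situation. SAP 9.1 has a rule for self-administration visits at which site personnel or a caregiver gave the injection. Protocol 13.4 names "Unexpected device malfunction leading to a failed or incomplete injection" as a possible reason to suspend or stop the study.

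Two programmers could follow the SAP faithfully and report different numerators and denominators. In the structural table the completion condition adds a second ambiguity for an injection that was interrupted. Read literally, the 11.3 sentence could also drop a pre-injection SIAQ that was validly completed before anyone injected.

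**Working it through.** **Figure to reproduce.** None. The documents give no expected device-failure rate, target or power for this outcome (SAP 2.4 says that no endpoint is powered). The check is therefore a reading of the text with an illustration of size.

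**Reading the text**

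| Question | SAP 11.3 | SAP 11.3.4 |
|---|---|---|
| Which assessments count? | Only those where the subject performed the self-injection | Those made after each injection |
| Denominator | Implied: devices from subject-performed injections | All devices used |
| Failed device, someone else then injects | Can be dropped | Counted |
| Which rule has priority? | Not stated | Not stated |

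The SAP also does not classify an injection that the subject starts and another person finishes, or repeats with a replacement device.

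**Inputs for the illustration**
- About 100 subjects per 1mL arm and 50 per 2mL arm (SAP 2.3.6).
- Two self-injection visits, Baseline and Week 8 (SAP 2.3.2).
- Two devices per visit in the 1mL cohort, one in the 2mL cohort (SAP 2.2.1).
- Planned devices: 100 × 2 × 2 = 400 per 1mL arm; 50 × 2 × 1 = 100 per 2mL arm. Replacements would add to these.
- Assumed: 1, 2 or 4 failed devices per arm after which someone else injected, and both visits pooled.

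**Formula.** The exact 90% interval for x of n has lower limit Beta(0.05; x, n−x+1) and upper limit Beta(0.95; x+1, n−x). For x = 0 the upper limit is 1 − 0.05^(1/n). For example, 1 − 0.05^(1/398) = 0.75% and 1 − 0.05^(1/98) = 3.01%.

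| Arm | Failures assumed | All used devices counted (11.3.4) | All of these failures dropped (11.3) |
|---|---|---|---|
| 1mL | 1 | 1/400 = 0.25% (0.01–1.18) | 0/399, upper limit 0.75% |
| 1mL | 2 | 2/400 = 0.50% (0.09–1.57) | 0/398, upper limit 0.75% |
| 1mL | 4 | 4/400 = 1.00% (0.34–2.27) | 0/396, upper limit 0.75% |
| 2mL | 1 | 1/100 = 1.00% (0.05–4.66) | 0/99, upper limit 2.98% |
| 2mL | 2 | 2/100 = 2.00% (0.36–6.16) | 0/98, upper limit 3.01% |
| 2mL | 4 | 4/100 = 4.00% (1.38–8.92) | 0/96, upper limit 3.07% |

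If only one of two failures is dropped, the 1mL arm shows 1/399 = 0.25% (0.01–1.18) and the 2mL arm 1/99 = 1.01% (0.05–4.70).

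**Direction.** Each dropped failure turns x/n into (x−1)/(n−1), which is smaller whenever x < n. Dropping an intact device that someone else operated turns x/n into x/(n−1), a negligible rise: 2/400 = 0.500% becomes 2/399 = 0.501%. The selective loss of failures is what matters.

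**The case against.** The strongest reply is that the specific rule should override the general one. SAP 11.3.4 names its own denominator and expects replacements, so a sensible programmer would count all used devices and nothing would be lost. That is a fair reading, but the SAP does not state it, and the 11.3 sentence admits no exception.

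Second, the scenario is inferred. The SAP nowhere says that an injection the subject starts and staff finish counts as not performed by the subject. The auto-injector descriptions (Protocol 7.1.2.1 and 7.1.4.1) have a locking shroud that deploys if skin contact is lost, so a replacement device is more likely than someone finishing on the same one. A failed device that the subject operated before replacement may still be counted. This stands, and it narrows the cases at risk.

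Third, a reader might infer that a device stopping mid-injection falls outside the integrity outcome altogether. The documents do not support that, because the functional-compromise entry has no completion condition. The ambiguity is confined to the structural table.

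Fourth, a reader might infer that such failures would vanish from the report. They would not. Device deficiencies include malfunctions (Protocol 11.1.1.3), are to be summarised in DV0002 (SAP 10.2), and all documented data are listed (SAP 3.1). What remains is that the planned summaries in SAP 10.2.1 and Protocol 14.5 cover adverse device effects only. No table, denominator or interval is specified for deficiencies.

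Fifth, the pre-injection SIAQ point is small. That form precedes injection, and subjects who never self-inject are already outside the FAS (SAP 3.6). A clarifying clause is enough.

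**Conclusion.** The SAP contains two counting rules for device integrity and does not rank them. If 11.3 is applied, failures that led someone else to inject can drop out of numerator and denominator, and the percentage is biased downward. If 11.3.4 governs, there is no effect.

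It would go too far to say that the plan removes failed devices. The 0/398 and 0/98 results are a worst case in which every assumed failure ends in another person injecting and every one is dropped. The failure counts are assumptions, and the intervals under the two rules overlap.

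This is an other outcome in a descriptive study with no threshold attached, so the primary result is not at stake. It still merits correction, because 11.3.4 supplies the only device-failure percentage with a planned confidence interval.

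**What to change.** Amend the SAP as follows:

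- **11.3:** state that the exclusion applies only to the post-injection SIAQ and the pain VAS. Keep a completed pre-injection SIAQ regardless of who then injected.
- **11.3.4, denominator:** in both the structural and the functional tables, count every investigational device used or attempted at the DV0002 Baseline and Week 8 self-injection visits. Include failed and replaced devices, whoever completed the injection, and show the operator as a row.
- **11.3.4, structural table:** define the completion wording to mean after use or attempted use. The phrase also stands in Protocol 4.1.3.1 and SAP 2.2.3.1, so record the interpretation in SAP 3.10.

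The restriction to those two visits is needed. SAP 2.3.2 has study personnel using the investigational device at Weeks 4, 12 and 16, while Protocol 5.1 has them using the 1mL PFS. Those passages must be reconciled separately. Without the restriction, scheduled staff doses could enter the denominator.

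The cost is a few sentences and minor table programming. Integrity is already recorded after each injection, and SAP 9.1 and 11.1 already rely on knowing who injected, so no new data should be needed. The downside is that the failure percentage may be slightly less favourable.

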### 11.3.1 Pre-injection SIAQ (versions 2.0 and 2.1)

The pre-injection SIAQ (versions 2.0 and 2.1) will be completed at DV0002 Baseline. Version 2.0 of the SIAQ will be used to assess bimekizumab-SS-1mL and bimekizumab-SS-2mL and version 2.1 of the SIAQ will be used to assess bimekizumab-AI-1mL and bimekizumab-AI-2mL. There are no differences in Version 2.0 to Version 2.1 in pre-injection SIAQ.

The pre-injection SIAQ consists of 7 items each with a scale of 1 to 5. There are three individual subscales (feelings about injections [FL, 3 items], self-confidence [CO, 3 items] and satisfaction with current mode of administration [SA, 1 item]). Each subscale score will be calculated using the average of the individual transformed item scores. The item score will be transformed using the following rule:

$$\text{Transformed Item Score} = ((\text{raw item score}) - 1) \times 2.5$$

In the case of missing values, no domain score will be calculated if more than 50% of the items within the domain are missing.

Higher individual scores of the pre-injection SIAQ indicate more confidence, higher satisfaction and less concerns with self-injections.

Summary statistics for all individual items and each subscale will be produced for Baseline.

### 11.3.2 Post-injection SIAQ (versions 2.0 and 2.1)

The post-injection SIAQ (versions 2.0 and 2.1) will be completed at DV0002 Baseline and DV0002 Week 8. Version 2.0 of the SIAQ will be used to assess bimekizumab-SS-1mL and bimekizumab-SS-2mL and version 2.1 of the SIAQ will be used to assess bimekizumab-AI-1mL and bimekizumab-AI-2mL. Version 2.0 and version 2.1 of the SIAQ are identical, except for Question 11 due to different handling of the devices.

The post-injection SIAQ consists of 21 items on 6 individual subscales (FL [3 items], self-image [IM, 1 item], CO [3 items], Injection-site reactions [RE, 2 items], ease of use [EU, 5 items) and satisfaction with self-injection [SA, 7 items]). The items of the individual subscale EU have a score range of 1 to 6, the other individual subscales have a score range of 1 to 5. Each subscale score will be calculated using the average of the individual transformed item scores. The item scores for the EU subscale will be transformed using the following rule:

---

$$\text{Transformed Item Score} = ((\text{raw item score}) - 1) \times 2$$

The item scores for the other subscales will be transformed using the following rule:

$$\text{Transformed Item Score} = ((\text{raw item score}) - 1) \times 2.5$$

In the case of missing values, no domain score will be calculated if more than 50% of the items within the domain are missing.

Higher individual scores of the post-injection SIAQ indicate more confidence, higher satisfaction and less concerns with self-injections.

Summary statistics for all individual items and each subscale will be produced for DV0002 Baseline and DV0002 Week 8.

### **11.3.3 Injection site pain**

The visual analog scale of injection site pain indicates the level of pain during the injection. It ranges from 0-100 mm with higher values indicating more severe pain and 0 for no pain.

Summary statistics of actual values and change from DV0002 Baseline values will be used to summarize injection site pain by visit after self-injection.

### **11.3.4 Structural and mechanical integrity of the devices**

The structural and mechanical integrity of the device after completion of self-injection will be assessed by the investigate after each injection in the "subject self-injection of bimekizumab" CRF page. The assessment will be done using the questions for structural integrity and function compromise. The structural integrity is based on a visual examination of the device that shows clear evidence of damage, compromised structural integrity not superficial and/or cosmetic imperfections. The functional compromise will be based on a visual examination of the device that shows clear evidence of damage and/or device dose not function normally. Both questions will be separately summarized.

Two injections will be performed at each self-injection visit. At each injection the device could be replaced. Percentages will be based on the total number of devices used.

Frequency tables will be produced to show the number and percentage of devices with:

- used bimekizumab-SS-1mL, bimekizumab-AI-1mL, bimekizumab-SS-2mL and bimekizumab-AI-2mL syringes identified as having structural integrity issues after completion of self-injection.
- used bimekizumab-SS-1mL, bimekizumab-AI-1mL, bimekizumab-SS-2mL and bimekizumab-AI-2mL syringes identified as functionally compromised.

The 90% CIs based on the Exact Binomial method will be reported as well.

---

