### 2.2 Study variables

#### 2.2.1 Primary outcome variable

The primary outcome variable is the percentage of subjects able to self-administer safe and effective injections using the 1mL bimekizumab safety syringe (bimekizumab-SS-1mL), 1mL bimekizumab auto-injector (bimekizumab-AI-1mL), 2mL bimekizumab safety syringe

(bimekizumab SS 2mL), or 2mL bimekizumab auto-injector (bimekizumab-AI-2mL), 8 weeks after training in self-injection technique. Safe and effective self-injection will be evaluated by the study personnel and is defined as:

- Complete dose delivery: Subject self-injects the complete dose of bimekizumab as confirmed by a visual inspection of the device which shows that the investigational medicinal product (IMP) is delivered completely (ie, container is empty), and
- No adverse device effects (ADEs) that would preclude continued use of the device for self-injection (ie, no serious adverse device effects (SADEs) and/or ADEs leading to withdrawal from the DV0002 substudy).

In the DV0002 substudy, for the 1mL devices the 320mg bimekizumab dose will be administered as two 160mg injections with either 2 bimekizumab-SS-1mL devices or 2 bimekizumab-AI-1mL devices. Each self-injection will be evaluated for safety and effectiveness by study personnel using the above criteria. The endpoint of safe and effective self-injection will be met only if both self-injections are determined to be safe and effective.

For the 2ml devices, the 320mg bimekizumab dose will be administered as 1 injection with either 1 bimekizumab-SS-2mL or 1 bimekizumab-AI-2mL device. Each self-injection will be evaluated for safety and effectiveness by study personnel using the above criteria. The endpoint of safe and effective self-injection will be met if the single self-injection is determined to be safe and effective.

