### **2.3.2 Treatment Period**

During the 16-week Treatment Period of DV0002, subjects will receive either bimekizumab 320mg Q8W or bimekizumab 320mg Q4W, based on their assigned dose at PS0014 Baseline. Baseline for DV0002 and Baseline for PS0014 will occur at the same time for the 1mL device cohort. In the 2mL device cohort, Baseline for DV0002 will occur at the PS0014 Week 24, Week 28, or Week 32 visit for subjects receiving bimekizumab Q4W or the PS0014 Week 24 or Week 32 visit for subjects receiving bimekizumab Q8W.

Eligible subjects (PS0014 entry criteria and DV0002 entry criteria) will be randomly assigned in a 1:1 ratio to perform self-injection using either the bimekizumab-SS-1mL or the bimekizumab-AI-1mL for the 1mL device cohort or using either the bimekizumab-SS-2mL or the bimekizumab-AI-2mL for the 2mL device cohort. Regardless of the assigned dose regimen, subjects will perform self-injection with the assigned device only at DV0002 Baseline and at DV0002 Week 8. For subjects in the bimekizumab 320mg Q4W dosing arm, injections will be administered by study personnel using the investigational device at Week 4 and Week 12; for subjects in both dosing arms, injections will be administered by study personnel using the investigational device at Week 16.

First treatment for the 1ml device cohort in PS0014 will be the timepoint of first bimekizumab injection in DV0002. First treatment in DV0002 will be the timepoint of first self-injection in DV0002.

After Week 16 in the DV0002 substudy, subjects will continue in PS0014.

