### **11.1 Primary outcome**

The primary outcome variable is the percentage of all subjects able to self-administer safe and effective injections using the given device at DV0002 Week 8. Safe and effective self-injection will be evaluated by the study personnel as defined below:

- Complete dose delivery: Subject self-injects the complete dose of bimekizumab as confirmed by a visual inspection of the investigational device which shows that the IMP is delivered completely (ie, container is empty), and
- No ADEs that would preclude continued use of the device for self-injection (ie, no SADEs and/or ADEs leading to withdrawal from the DV0002 substudy).

All data to assess the primary outcome is collected on the subject self-injection of bimekizumab CRF page for DV0002 Week 8. For the number of subjects with safe and effective self-injections simply the cases which indicated “yes” for the question “Did the subject self-inject the complete dose of Bimekizumab” and “no” for the question “Where there any AEs related to use of the investigational device for self-injection” at Week 8 are counted.

For subjects in the 1mL device cohort, two self-injections will be performed at DV0002 Week 8 and the questions will be answered twice. If the answers are different between both self-injections in one visit, then the worst case of both answers will be used for analysis at this visit. Subjects with only one self-injection at one visit will be counted as non-responder. Assessments where the self-injection was not performed by the subject will be not included in any summary statistics.

The number and percentage of subjects with safe and effective self-injections will be tabulated separately for each device overall and within each device by dosing regimen. The 90% CIs based on the Exact Binomial method will be reported as well.

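### The 90% exact interval for device integrity treats every used device as independent, so a pooled 1mL interval can be too narrow if issues cluster within subjects

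*SAP*

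**What the plan says.** Protocol 4.1.3.1 defines the outcome per device: "Percentage of used devices identified as having structural or mechanical integrity issues after completion of self-injection". SAP 11.3.4 follows this ("Percentages will be based on the total number of devices used") and adds: "The 90% CIs based on the Exact Binomial method will be reported as well". It summarises two questions separately, structural integrity and functional compromise.

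On how many devices a subject supplies, SAP 11.3.4 says: "Two injections will be performed at each self-injection visit. At each injection the device could be replaced". SAP 2.2.1 confirms two devices per dose for the 1mL cohort ("administered as two 160mg injections with either 2 bimekizumab-SS-1mL devices or 2 bimekizumab-AI-1mL devices") and one for the 2mL cohort. SAP 2.3.2 gives two self-injection occasions: "subjects will perform self-injection with the assigned device only at DV0002 Baseline and at DV0002 Week 8".

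SAP 11.3.4 does not say whether its tables pool Baseline and Week 8. Protocol 4.1.3.1 specifies presentation by visit for the post-injection SIAQ and for pain, but not for the device percentage. For the 1mL primary outcome, SAP 11.1 reduces two differing injection results to one: "then the worst case of both answers will be used for analysis at this visit".

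**The concern.** The exact binomial interval is valid for independent trials. Devices used by the same person share handling technique, training, injection sites and the staff who inspect them, so an issue with one may make an issue with another more likely. Protocol 11.1.1.3 counts use errors among device deficiencies, and one of the two tabulated questions asks whether the device functioned normally, which technique can affect. Clustering is plausible but not certain: each injection uses a new device, and manufacturing faults need not follow the subject.

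Protocol 14.2 describes an estimation study without hypothesis testing. The interval is therefore the only statement of precision for device integrity, which is a stated objective in Protocol 3.3. A reader would take its upper limit as the bound on the device problem rate. If issues cluster, that bound claims more information than the number of independent users supports.

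**Working it through.** The plan states no expected issue rate, interval width or power for this outcome, so it has no figure to reproduce.

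**Inputs from the documents**
- Subjects per arm (SAP 2.3.6): about 100 (1mL) and about 50 (2mL).
- Devices per subject: 2 × 2 = 4 (1mL) and 1 × 2 = 2 (2mL), before any replacement.
- Devices per 1mL arm: 100 × 4 = 400 pooled, or 100 × 2 = 200 by visit. Per 2mL arm: 50 × 2 = 100 pooled, or 50 by visit.
- Interval: two-sided 90% Clopper-Pearson, 5% in each tail.

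**Assumed:** issue rate *p* of 0.5 to 5%; ICC of 0 to 0.5.

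**Step 1. One worked interval.** Take 8 affected devices out of 400 (2%). The planned interval is 1.00 to 3.58%. With *m* devices per subject, the design effect is 1 + (*m* − 1) × ICC. At ICC 0.2 and *m* = 4 this is 1 + 3 × 0.2 = 1.6, so the effective sample size is 400 / 1.6 = 250. Clopper-Pearson on 250 at the same 2% gives 0.79 to 4.16%.

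**Step 2. Coverage of the planned interval, 1mL pooled (100 × 4).** Each subject's count is beta-binomial. The distribution of the arm total is obtained exactly by convolution over subjects, and coverage is the probability that the nominal 90% interval contains *p*.

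| Issue rate | ICC 0 | ICC 0.1 | ICC 0.2 | ICC 0.3 |
|---|---|---|---|---|
| 0.5% | 98.4% | 96.8% | 95.4% | 94.1% |
| 1% | 96.1% | 93.1% | 89.9% | 86.4% |
| 2% | 92.6% | 88.3% | 84.2% | 80.2% |
| 5% | 91.7% | 87.2% | 82.9% | 79.1% |

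At 0.5% coverage is still 92.0% at ICC 0.5, because the exact method is conservative for rare events. At a 2% rate and ICC 0.3, the true rate lies above the reported upper limit with probability 11.0%, against a nominal maximum of 5%. Independent simulation (40,000 runs per setting) at rates of 1, 2 and 5% agrees to within 0.3 points.

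**Step 3. Two devices per subject.** Over the same rates plus 3%, and up to ICC 0.3, the lowest coverage is about 89% for 1mL tables by visit (100 × 2, at 5%) and about 87% for 2mL pooled (50 × 2, at 3%). A 2mL table by visit has one device per subject barring replacement, so clustering does not arise.

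**Step 4. A cluster-adjusted interval (100 × 4).** The design effect is estimated as the between-subject variance of the proportion over the binomial variance, floored at 1, with Clopper-Pearson on the effective sample size. Simulated coverage at ICC 0 / 0.1 / 0.2 / 0.3:
- 1% rate: 96.3 / 94.3 / 92.5 / 90.8%, against 96.3 / 93.3 / 89.6 / 86.5% for the planned interval in the same simulation.
- 2% rate: 92.7 / 90.9 / 89.8 / 88.8%.
- 5% rate: 92.5 / 91.9 / 91.5 / 91.7%.

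**The case against.** The case against acting is mainly about relevance. A shortfall needs pooled visits, a rate of about 1% or more and appreciable clustering, and the documents establish none of these. The ICC values also imply strong dependence. Given one affected device, the chance that another from the same subject is affected is *p* + ICC × (1 − *p*). At a 1% rate and ICC 0.2 that is 0.01 + 0.2 × 0.99 = 20.8%, about 21 times the base rate. If the within-subject risk is merely tripled, pooled 1mL coverage is 95.5% at a 1% rate and 90.9% at 2%, and falls below nominal (86.9%) only at 5%. Nothing in the documents supports the larger multiples. This stands as a limit on how large the effect is likely to be.

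The pooling reading is also open. SAP 11.3.4 sets its denominator directly after describing what happens at each visit, which could equally mean tables by visit. That stands, and it is a reason for the SAP to say which is meant.

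The comparison with SAP 11.1 is imperfect: the worst-case rule there implements an endpoint that requires both injections to succeed, and is not a clustering correction. That is fair. It does mean that the question does not arise for the primary outcome but does for this one.

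Finally, a design effect estimated from a handful of events is noisy. At a 1% rate and ICC 0.2 it sits at or near its floor of 1 in about 45% of simulated trials. Average coverage nevertheless improves at that rate (Step 4), and for 2mL pooled (50 × 2) the adjusted interval did not cover less than the planned one in any setting run. The noise does not defeat the remedy.

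**Conclusion.** The concern holds in its conditional form. The planned interval assumes independent devices, a 1mL subject supplies four, and no allowance is made. With visits pooled, coverage falls below 90% between ICC 0 and 0.1 at a 5% rate, a little below 0.1 at 2%, and at about 0.2 at 1%. There is no shortfall at 0.5%, and only a small one where each subject contributes two devices. These figures rest on an assumed issue rate and ICC, on a beta-binomial model and on pooling, which the SAP does not state.

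This is an outcome in the other category, with no test, threshold or sample-size target attached, so no trial conclusion changes. The effect is on the precision claimed for device reliability, and the change is a worthwhile refinement rather than a necessary correction.

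**What to change.** In SAP 11.3.4:

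1. State whether the integrity tables pool Baseline and Week 8 or are by visit.
2. Keep the protocol's device-level percentage, but give it a 90% interval that treats the subject as the cluster. One option is Clopper-Pearson on the effective sample size, with the design effect estimated from subject-level variance and floored at 1.
3. Add one row for the number and percentage of subjects with at least one affected device, with its own exact 90% interval. This removes within-subject dependence and needs no ICC.
4. Limit the sentence on two injections per visit to the 1mL cohort, because SAP 2.2.1 gives the 2mL dose as one injection.

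The cost is SAP wording, a short program change and one extra row per table. The downside is width. At a 2% rate (100 × 4) the adjusted interval averages 2.60 points against 2.55 with no clustering, and 3.51 against 2.51 at ICC 0.3. With no affected devices the design effect cannot be estimated and the planned exact interval is kept.
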